 - The QTc is the QT interval corrected for heart rate according to either Bazett's formula (QTcB), Fridericia's formula (QTcF), or another method, machine or manual over read.
 - The specific formula that will be used to determine eligibility and discontinuation for an individual subject should be determined prior to initiation of the study. In other words, several different formulae cannot be used to calculate the QTc for an individual subject and then the lowest QTc value used to include or discontinue the subject from the trial. For purposes of data analysis, QTcB, QTcF, another QT correction formula, or a composite of available values of QTc will be used as specified in the Reporting and Analysis Plan (RAP).
7. ALT >2xULN and bilirubin >1.5xULN (isolated bilirubin >1.5xULN is acceptable if bilirubin is fractionated and direct bilirubin <35%) at screening.
8. Current or chronic history of liver disease, or known hepatic or biliary abnormalities (with the exception of Gilbert's syndrome or asymptomatic gallstones).

9. Current or history of renal disease or estimated glomerular filtrate rate (GFR) by Chronic Kidney Disease Epidemiology Collaboration equation (CKD-EPI) <60 mL/min/1.73 m².
10. Hereditary or acquired immunodeficiency disorder, including immunoglobulin deficiency.
11. A major organ transplant (e.g., heart, lung, kidney, liver) or hematopoietic stem cell/marrow transplant.
12. A planned surgical procedure that, in the opinion of the investigator, makes the subject unsuitable for the study.
13. A history of malignant neoplasm within the last 5 years, except for adequately treated cancers of the skin (basal or squamous cell carcinoma) or carcinoma in situ of the uterine cervix that has been fully treated and shows no evidence of recurrence.
14. A history of hypertrophic scarring or keloid formation, or known allergy to lidocaine or other local anaesthetics.

CONCOMITANT MEDICATIONS

15. The subject has received treatment with the therapies listed in Section 6.11, or changes to those treatments, within the specified timeframe. If in doubt, or the therapy is not listed please consult with the medical monitor.
 - Other medications (including vitamins, herbal and dietary supplements) will be considered on a case-by-case basis, and will be allowed if in the opinion of the investigator the medication will not interfere with the study procedures or compromise subject safety.

RELEVANT HABITS

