5.4. Withdrawal/Stopping Criteria

Subjects may be withdrawn from the study for any of the following reasons:

- A subject may withdraw from study treatment at any time at his/her own request, or may be withdrawn at any time at the discretion of the investigator for safety, behavioural or administrative reasons. If a subject withdraws from the study, he/she may request destruction of any samples taken, and the investigator must document this in the site study records. The reason for withdrawal should be documented in the Case Report Form (CRF).

- The Sponsor may request a subject withdraw for reasons such as significant protocol deviations (after discussion with the investigator).
- If a subject is withdrawn from study treatment, this subject is also considered to be withdrawn from the study.
- Study is terminated by the Sponsor.

If a subject is withdrawn, the Sponsor may decide to replace that subject and this will be done through the Interactive Response Technology System (IRTS).

The following actions must be taken in relation to a subject who fails to attend the clinic for a required study visit:

- The site must attempt to contact the subject and re-schedule the missed visit as soon as possible.
- The site must counsel the subject on the importance of maintaining the assigned visit schedule and ascertain whether or not the subject wishes to and/or should continue in the study.
- In cases where the subject is deemed ‘lost to follow up’, the investigator or designee must make every effort to regain contact with the subject (where possible, 3 telephone calls and if necessary a certified letter to the subject’s last known mailing address or local equivalent methods). These contact attempts should be documented in the subject’s medical record.
- Should the subject continue to be unreachable, only then will he/she be considered to have withdrawn from the study with a primary reason of “Lost to Follow-up”.

If a subject chooses to withdraw from the study after dosing, the investigator must make every effort to complete the follow up assessments detailed in the Time and Events Table (Section 7.1).

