5.4.3.1. Study Treatment Restart or Rechallenge

Study treatment restart or rechallenge after liver chemistry stopping criteria are met by any subject participating in this study is not allowed.

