7.1. Time and Events Table

Procedures	Screening	Treatment Period												Early Withdrawal ¹⁴	Follow Up	Notes	
		Day 1	Day 8	Day 15	Day 22	Day 29	Day 36	Day 43 (week 6)	Day 50	Day 57	Day 64	Day 71	Day 78				
Screening Procedures																Visit windows Screening: up to 30d before Day 1. Treatment Period (except Day 1 & 85): ± 3d. Day 1 NA; Day 85 ± 2d. Early Withdrawal: NA Follow Up: 28d after last dose ± 3d	
Site Visit	X	X	X	X		X		X		X		X		X	X		
Phone call					X		X		X		X		X				
Safety Assessments																1. Full physical exam: height/weight at Screening, height not required at later timepoints. 2. Vitals: BP, HR, RR, temperature. ECG triplicate at Screening only. 3. Urinalysis not required on Days 29, 57 and 71. 4. If urine test is positive, confirmatory serum test must be performed. 5. Pre-dose 6. In Cohort 1, subjects must take study medication twice a day approx. 12h apart. In Cohort 2, subjects must take study medication three times a day approx. 8h apart. Exact time of dosing to be recorded in diary cards. On Days 43 and 85, subjects must not take medication at home in the morning. Subjects will complete pre-dose assessments and then will be administered their morning dose of medication at site on Day 43 only. On Day 85, subjects no longer dosed. 7. Diary card checked by site staff and new diary card dispensed at every study visit. 8. Blood samples for inflammatory	
Full physical exam ¹	X													X	X	X	
Brief physical exam		X ⁵		X		X		X ⁵		X		X					
12-lead ECG, vital signs ²	X	X ⁵	X	X		X		X ⁵		X		X		X	X	X	
Columbia Suicide Severity Rating Scale (C-SSRS)	X	X ⁵						X ⁵						X	X		
Hematology, chemistry, urinalysis	X	X ⁵	X	X		X ³		X ⁵		X ³		X ³		X	X	X	
FSH & estradiol (if applicable)	X																
Serum pregnancy (WCBP)	X																
Urine pregnancy test (WCBP only) ⁴			X ⁵	X	X		X		X ⁵		X		X	X	X		
Study Treatment																	
Randomisation		X															
Study medication ⁶		X	X														
Dispensing of study medication		X				X				X							
Dispensing of diary cards ⁷	X	X	X		X		X		X		X		X				
PROs/ Disease Assessments																	

Procedures	Screening	Treatment Period												Early Withdrawal ¹⁴	Follow Up	Notes
		Day 1	Day 8	Day 15	Day 22	Day 29	Day 36	Day 43 (week 6)	Day 50	Day 57	Day 64	Day 71	Day 78	Day 85 (week 12)		
Psoriatic Body Surface Area	X	X ⁵												X	X	
PASI, PGA, PLSS, Itch	X	X ⁵		X		X		X ⁵		X		X		X	X	
DLQI	X	X ⁵						X ⁵						X	X	
Photograph of lesions		X ⁵						X ⁵						X	X	

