12.2. Appendix 2: Liver Safety Required Actions and Follow up Assessments

Phase II liver chemistry stopping and increased monitoring criteria have been designed to assure subject safety and evaluate liver event etiology (in alignment with the FDA premarketing clinical liver safety guidance).

<http://www.fda.gov/downloads/Drugs/GuidanceComplianceRegulatoryInformation/Guidances/UCM174090.pdf>.

Phase II liver chemistry stopping criteria and required follow up assessments

Liver Chemistry Stopping Criteria – Liver Stopping Event	
ALT-absolute	ALT \geq 5xULN
ALT Increase	ALT \geq 3xULN persists for \geq 4 weeks
Bilirubin^{1, 2}	ALT \geq 3xULN and bilirubin \geq 2xULN ($>35\%$ direct bilirubin)
INR²	ALT \geq 3xULN and INR >1.5 , if INR measured
Cannot Monitor	ALT \geq 3xULN and cannot be monitored weekly for 4 weeks
Symptomatic³	ALT \geq 3xULN associated with symptoms (new or worsening) believed to be related to liver injury or hypersensitivity

Required Actions and Follow up Assessments following ANY Liver Stopping Event

Actions	Follow Up Assessments

 • Immediately discontinue study treatment • Report the event to GSK within 24 hours • Complete the liver event CRF and complete an SAE data collection tool if the event also meets the criteria for an SAE² • Perform liver event follow up assessments • Monitor the subject until liver chemistries resolve, stabilize, or return to within baseline (see MONITORING below) • Do not restart/rechallenge subject with study treatment unless allowed per protocol and GSK Medical Governance approval is granted • If restart/rechallenge not allowed per protocol or not granted, permanently discontinue study 	
 • Viral hepatitis serology⁴ • Blood sample for pharmacokinetic (PK) analysis, obtained within 2 days after last dose⁵ • Serum creatine phosphokinase (CPK) and lactate dehydrogenase (LDH). • Fractionate bilirubin, if total bilirubin \geq 2xULN • Obtain complete blood count with differential to assess eosinophilia • Record the appearance or worsening of clinical symptoms of liver injury, or hypersensitivity, on the AE report form • Record use of concomitant medications

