
treatment and may continue subject in the study for any protocol specified follow up assessments
 
MONITORING:
 
For bilirubin or INR criteria:
 
 Repeat liver chemistries (include ALT, AST, alkaline phosphatase, bilirubin) and perform liver event follow up assessments within 24 hrs Monitor subjects twice weekly until liver chemistries resolve, stabilize or return to within baseline A specialist or hepatology consultation is recommended 
For All other criteria:
 
 Repeat liver chemistries (include ALT, AST, alkaline phosphatase, bilirubin) and perform liver event follow up assessments within 24-72 hrs Monitor subjects weekly until liver chemistries resolve, stabilize or return to within baseline 	
on the concomitant medications report form including acetaminophen, herbal remedies, other over the counter medications.
 
 Record alcohol use on the liver event alcohol intake case report form 
For bilirubin or INR criteria:
 
 Anti-nuclear antibody, anti-smooth muscle antibody, Type 1 anti-liver kidney microsomal antibodies, and quantitative total immunoglobulin G (IgG or gamma globulins). Serum acetaminophen adduct HPLC assay (quantifies potential acetaminophen contribution to liver injury in subjects with definite or likely acetaminophen use in the preceding week [James, 2009]). NOTE: not required in China Liver imaging (ultrasound, magnetic resonance, or computerised tomography) and /or liver biopsy to evaluate liver disease: complete Liver Imaging and/or Liver Biopsy CRF forms.
---	---

1. Serum bilirubin fractionation should be performed if testing is available. If serum bilirubin fractionation is not immediately available, discontinue study treatment for that subject if ALT \geq 3xULN **and** bilirubin \geq 2xULN. Additionally, if serum bilirubin fractionation testing is unavailable, **record presence of detectable urinary bilirubin on dipstick**, indicating direct bilirubin elevations and suggesting liver injury.

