
 Medical or scientific judgment should be exercised in deciding whether reporting is appropriate in other situations, such as important medical events that may not be immediately life-threatening or result in death or hospitalization but may jeopardize the subject or may require medical or surgical intervention to prevent one of the other outcomes listed in the above definition. These should also be considered serious. Examples of such events are invasive or malignant cancers, intensive treatment in an emergency room or at home for allergic bronchospasm, blood dyscrasias or convulsions that do not result in hospitalization, or development of drug dependency or drug abuse
g. Is associated with liver injury and impaired liver function defined as:

 ALT \geq 3xULN and total bilirubin[*] \geq 2xULN (>35% direct), or ALT \geq 3xULN and INR^{**} $>$ 1.5.

* Serum bilirubin fractionation should be performed if testing is available; if unavailable, measure urinary bilirubin via dipstick. If fractionation is unavailable and ALT \geq 3xULN and total bilirubin \geq 2xULN, then the event is still to be reported as an SAE.
 
** INR testing not required per protocol and the threshold value does not apply to subjects receiving anticoagulants. If INR measurement is obtained, the value is to be recorded on the SAE form.

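### Exclusion 7 joins its ALT and bilirubin limits with 'and', so read literally it admits isolated ALT above 2xULN, and no other entry criterion sets a numeric ALT limit

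*Protocol*

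**What the plan says.** Section 5.2 makes a subject ineligible if any one numbered exclusion applies. Exclusion 7 is a single item: "ALT >2xULN and bilirubin >1.5xULN (isolated bilirubin >1.5xULN is acceptable if bilirubin is fractionated and direct bilirubin <35%) at screening".

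The other entry criteria that touch the liver carry no ALT number. Exclusion 8 concerns liver disease and recognised liver or biliary abnormality, exclusion 22 is hepatitis serology, and inclusion 2 leaves other medical conditions to the investigator's judgement. The numeric laboratory limits in exclusion 21 are for haematology only. Section 5 allows no deviation from the criteria, and Section 7 allows no waivers apart from immediate safety concerns.

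On treatment, Appendix 2 (Section 12.2) stops dosing on several ALT rules. One is "ALT \geq 3xULN persists for \geq 4 weeks". Section 5.4.3.1 then adds: "Study treatment restart or rechallenge after liver chemistry stopping criteria are met by any subject participating in this study is not allowed".

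**The concern.** A screening limit on ALT normally excludes on its own. Here it does so only when bilirubin is raised as well. A site that applies the criterion exactly as written, as Section 5 requires, has no numeric ground for turning away a subject with isolated raised ALT, and sites may differ in how they use their judgement.

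The stopping thresholds are multiples of the upper limit of normal and are not relative to the subject's own baseline. A subject who enters with ALT already at or above 3xULN can therefore reach a stopping rule simply by staying the same. At stake are an avoidable treatment stop, and a liver event that reflects the baseline, in a small study whose primary objective is safety.

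**Working it through.** No statistical figure is involved. The check is a logic table, a comparison of wording and a count of days.

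**1. What exclusion 7 does under each connector**

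| Screening result | 'and', literal | 'or' |
|---|---|---|
| ALT >2x, bilirubin >1.5x | excluded | excluded |
| ALT >2x, bilirubin ≤1.5x | **not excluded** | excluded |
| ALT ≤2x, bilirubin >1.5x | not excluded by the connector alone | excluded unless fractionated with direct <35% |
| Neither | not excluded | not excluded |

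The second row is the defect. The third row shows why 'or' was evidently meant: if both elevations were required, isolated bilirubin could never exclude anyone, and the exception for it would have nothing to act on.

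**2. How the protocol uses the same form elsewhere**

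The bilirubin row of Appendix 2 reads "ALT \geq 3xULN and bilirubin \geq 2xULN", and item g of the SAE definition (Section 12.4.2) begins "ALT \geq 3xULN and total bilirubin". In both places the two conditions must hold together. Where nearby exclusions intend alternatives they use 'or' (exclusions 6 and 9) or semicolons (exclusion 21). A joint reading of exclusion 7 is therefore consistent with the protocol's own usage.

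**3. What follows at each level of isolated ALT (bilirubin within its limit)**

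| Screening ALT | Literal rule | Separate limits | If stable on treatment |
|---|---|---|---|
| ≤2xULN | passes | passes | no ALT stop |
| >2 to <3xULN | passes | excluded | no ALT stop |
| 3 to <5xULN | passes | excluded | stops once it has lasted 4 weeks |

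**4. When the 4-week rule would be met**

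Inputs: the Time and Events Table (Section 7.1), row "Hematology, chemistry, urinalysis", schedules chemistry at Days 1 (pre-dose), 8, 15, 29 and 43. Visits between Day 1 and Day 85 have a window of ±3 days. Four weeks is 28 days.

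- Day 1 to Day 29: 29 − 1 = 28 days, range 25 to 31. The rule is met at the nominal visit, but may be missed if the visit is early.
- Day 1 to Day 43: 43 − 1 = 42 days, range 39 to 45. The rule is met at any visit within the window.
- Counting only from the first post-dose sample, Day 8 to Day 43: 43 − 8 = 35 days. With both windows at their extremes the shortest interval is 35 − 6 = 29 days, which still meets the rule.

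A stable value of 3 to <5xULN therefore meets the rule at Day 29, or at the latest at Day 43.

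**The case against.** The strongest reply is that the sentence explains itself. Because the isolated-bilirubin exception works only with separate limits, a sensible investigator would infer 'or'. The comparison with Appendix 2 and the SAE definition is also imperfect: those joint conditions carry no exception for an isolated value, and Appendix 2 deals with ALT alone in rows of its own. Exclusion 8 reaches recognised abnormalities as well as disease history, inclusion 2 covers conditions that would disturb study assessments, and Section 7.3 makes the investigator responsible for judging out-of-range results. Any of these could keep out a subject with clearly raised ALT.

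Much of this stands. It makes the point a drafting slip with a recoverable meaning, not a deliberate choice to admit raised ALT, and it narrows the number of subjects affected. It does not supply the missing number: the cover rests on judgement, while Section 5 tells sites to follow the criteria as specified.

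Stronger readings are tempting but not supported:

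- A reader might infer that one such stop widens the safety intervals in Table 4. Any single event of any kind would do that, and under Section 12.4.1 a pre-existing condition that does not worsen would not ordinarily be an adverse event.
- A reader might infer that subjects with ALT of 5xULN or more would enter and stop at once. Exclusion 7 read literally does not bar them, but exclusion 8 or inclusion 2 probably would. The documents give no ALT level at which that judgement takes over.
- A reader might infer that the subject is lost from the study. Section 5.4 points that way ("If a subject is withdrawn from study treatment, this subject is also considered to be withdrawn from the study"), but after a liver stop Appendix 2 says the site "may continue subject in the study for any protocol specified follow up assessments".
- A reader might infer a matching gap for bilirubin. The parenthesis can be read as already barring isolated raised bilirubin unless it is fractionated with a low direct share, so no such gap is shown.

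**Conclusion.** The criterion is wrong as written: literally applied, it does not exclude isolated ALT above 2xULN, and nothing else in the entry criteria sets a numeric ALT limit. For values above 2 and below 3xULN the effect is on eligibility only. The practical consequence lies at 3 to <5xULN, where a stable value could end treatment by Day 43 at the latest without any drug effect.

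This rests on three assumptions: the site reads the criterion literally, the investigator does not exclude the subject on judgement, and ALT stays at or above 3xULN. How often all three would hold cannot be derived from the protocol. The point is modest in size but concerns an eligibility threshold in a study whose primary objective is safety, so it should be corrected.

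**What to change.** In exclusion 7, replace 'and' with 'or'. Clearer still, use two lines:

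- (a) ALT >2xULN at screening;
- (b) bilirubin >1.5xULN at screening, except that an isolated elevation is acceptable if bilirubin has been fractionated and the direct part is <35%.

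This puts the ALT entry limit (2xULN) below the 3xULN level of the persistence rule and gives the bilirubin exception a function. The cost is a one-word or two-line edit and possibly a few more screen failures. Section 5.3 already lets a failing screening laboratory test be repeated once within the screening window, so a passing rise in ALT need not cost a subject.

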5.3. Screening/Baseline/Run-in Failures

Screen failures are defined as subjects who consent to participate in the clinical trial but are never subsequently randomized. In order to ensure transparent reporting of screen failure subjects, meet the Consolidated Standards of Reporting Trials (CONSORT) publishing requirements, and respond to queries from Regulatory authorities, a minimal set of screen failure information is required including Demography, Screen Failure details, Eligibility Criteria, and Serious Adverse Events (see Section 7.3.1.5).

Subjects who do not qualify to participate in the study due to a screening laboratory value or ECG abnormality can repeat the test once within the original screening time window, if the Investigator believes there is a reasonable possibility that the subject would be eligible if re-tested.

Subjects can be re-screened only on approval of the GSK Medical Monitor and only once. Re-screening is allowed when a subject failed inclusion/exclusion criteria or some other screening condition initially, but the Investigator believes there is a reasonable probability that the subject would be eligible if re-screened.

5.4. Withdrawal/Stopping Criteria

Subjects may be withdrawn from the study for any of the following reasons:

- A subject may withdraw from study treatment at any time at his/her own request, or may be withdrawn at any time at the discretion of the investigator for safety, behavioural or administrative reasons. If a subject withdraws from the study, he/she may request destruction of any samples taken, and the investigator must document this in the site study records. The reason for withdrawal should be documented in the Case Report Form (CRF).

- The Sponsor may request a subject withdraw for reasons such as significant protocol deviations (after discussion with the investigator).
- If a subject is withdrawn from study treatment, this subject is also considered to be withdrawn from the study.
- Study is terminated by the Sponsor.

If a subject is withdrawn, the Sponsor may decide to replace that subject and this will be done through the Interactive Response Technology System (IRTS).

The following actions must be taken in relation to a subject who fails to attend the clinic for a required study visit:

- The site must attempt to contact the subject and re-schedule the missed visit as soon as possible.
- The site must counsel the subject on the importance of maintaining the assigned visit schedule and ascertain whether or not the subject wishes to and/or should continue in the study.
- In cases where the subject is deemed ‘lost to follow up’, the investigator or designee must make every effort to regain contact with the subject (where possible, 3 telephone calls and if necessary a certified letter to the subject’s last known mailing address or local equivalent methods). These contact attempts should be documented in the subject’s medical record.
- Should the subject continue to be unreachable, only then will he/she be considered to have withdrawn from the study with a primary reason of “Lost to Follow-up”.

If a subject chooses to withdraw from the study after dosing, the investigator must make every effort to complete the follow up assessments detailed in the Time and Events Table (Section 7.1).

